### 7.3 Infusion Days (+ 1 to + 4) – Cohorts 1-5

### 7.3.1 **Before Infusion (Morning of Day + 1)**

- Review concomitant medications
- CTNI to conduct HAMD17 interview
- EPDS

- STAI6
- Assess CGI-S
- Collect AEs
- Collect vital signs (BP, pulse, temperature, pulse oximetry, respiratory rate)
- Stanford Sleepiness Scale (SSS)
- Conduct CSSRS interview
- Randomization
- Start monitoring of pulse oximetry
- The subject's bed should be placed close to the nursing station in an area that allows visual observation of the subject throughout the infusion period.

### 7.3.2 **During Infusion (Days +1 to +4)**

- Start bolus/infusion in the morning of Day +1 (0h) after baseline assessments are completed
- CTNI to conduct interviews for HAMD17 (+12h, +24h, +48h, +60h, +72h)
- Conduct interviews for CGI-I (+12h, +24h, +48h, +60h, +72h)
- EPDS (+60h)
- STAI6 (+12h, +24h, +48h, +60h, +72h)
- Collect AEs
- Collect ECG (+12h, +24h, +48h, +72h)
- Collect VS (BP, pulse, respiratory rate, pulse oximetry, temperature): (+4, +8h, +12, +18h, +24h, +32h, +40h, +48h, +56h, +60h, +72h)
- Collect SSS (+8h, +32h, +56h, +72h)
- Collect pharmacokinetic samples (+12h, +24h, +48h, +72h)
- Record concomitant medications
- Lower the infusion rate to half what was prescribed for the cohort (for example, lower the infusion rate from 4 mg/h to 2 mg/h) (+48h)
- Collect safety laboratory tests (+48h)
- Collect neurosteroid level (+48h)
- End infusion (+60h)
- Collect urine sample for urinalysis, drug screen and urine pregnancy test (+72h)
- Conduct CSSRS interview (+12h, +36h, +60h, +72h)
- Perform a physical examination (+72h)

- Stop monitoring of pulse oximetry and Q15 min health checks (+72h)
- Discharge subject (+72h)

## 7.4 Post Discharge Follow-up Period (Days +5 to +30) – Cohorts 1-5

# 7.4.1 First Post-discharge Visit 7 Days After Discharge from the Unit (Day +11; visit window)

- Review concomitant medications and therapies
- Collect vital signs (BP, pulse, temperature, pulse oximetry, respiratory rate)
- Collect safety laboratory tests.
- Collect neurosteroid level
- Collect pharmacokinetic sample
- Collect urine sample for urinalysis, drug screen and urine pregnancy test
- Measure weight
- Conduct interviews for HAMD17 (CTNI) and CGI-I
- EPDS
- STAI6
- Conduct CSSRS interview
- Collect AEs

# 7.4.2 Second Post-discharge Visit 30 Days After Discharge From the Unit (Day +34)

- Review concomitant medications and therapies
- Collect vital signs (BP, pulse, temperature, pulse oximetry, respiratory rate)
- Measure weight
- Collect urine sample for urinalysis, drug screen and urine pregnancy test,
- Collect pharmacokinetic sample
- Conduct CSSRS interview
- Collect AEs
- Conduct interviews for HAMD17 (CTNI) and CGI-I
- EPDS
- STAI6

# Table 1. Schedule of Assessments – Cohorts 1-5

Day	Day -14 to -1	Day 0	Day 1 (Start Infusion in AM, 0h)	Day 2	Day 3 (End Infusion in PM)		Day 11 (Day 7 Post Discharge)	Day 34 (Post Discharge Day 30)
VISIT	Screening	Admission	Infusion	Infusion	Infusion	Discharge	Follow-up	Follow-up
			0h-24	24-48h	48-72	72h		
Informed consent	Х							
Demographics, Medical History	Х							
MINI neuropsychiatric interview	Х							
Inclusion/Exclusion criteria	Х	Х						
Concomitant Meds and Therapy Review	X	Х	Х	Х	Х	Х	Х	Х
Admission to the unit		Х						
Discharge from the unit						Х		
Physical examination	Х					Х		
SAFER Interview (during screening)	Х							
Vital signs (BP, Pulse, pO2, RR, temp)	X	Х	Х	Х	X	Х	Х	Х
Height (screening only) and weight	X	Х					Х	Х
ECGs	X	Х	X	Х	X	Х		
Safety Laboratory Tests	Х	Х			Х		Х	
Neurosteroid level		Х			X		Х	
Urinalysis, Drug Screen and Pregnancy Tests	Х	Х				Х	Х	Х
CSSRS	Х	Х	Х	Х	X	Х	Х	Х
Record AEs		Х	Х	Х	Х	Х	Х	Х
Randomization			Х					
Start bolus/infusion (0h)			Х					
Lower the infusion rate to half (+48h)					Х			
End infusion (+60h)					Х			
PK sample collection			Х	Х	Х	Х	Х	Х
HAMD17	Х	Х	Х	Х	Х	Х	Х	Х
CGI-I			Х	Х	X	Х	Х	Х
CGI-S	Х		Х					
EPDS	Х		Х		Х		Х	Х
SSS			Х	Х	Х	Х		
STAI6	Х		Х	Х	Х	Х	Х	Х
Q15 min health checks & pulse ox				throug	hout			

Marinus Pharmaceuticals, Inc. Protocol 1042-PPD-2002

#### Specific timepoints for assessments on days +1, +2, +3 and +4: - Cohorts 1-5

PK samples: +12h, +24h, +48h, +72h HAMD17: before start of infusion, +12h, +24h, +48h, +60h, +72h all done by CTNI CGI-I: +12h, +24h, +48h, +60h, +72h CGI-S: before start of infusion EPDS: before start of infusion, +60h STAI6: before start of infusion, +12h, +24h, +48h, +60h, +72h ECG: +12h, +24h, +48h, +72h Vital Signs: (BP/P/pO2/RR/Temp): before start of infusion, +4, +8h, +12, +18h, +24h, +32h, +40h, +48h, +56h, +60h, +72h SSS: before start of infusion, +8h, +32h, +56h, +72h CSSRS: before start of infusion, +12h, +36h, +60, +72h Safety laboratory tests and neurosteroid level: +48h Urinalysis drug and pregnancy test: +72h Physical examination: +72h AEs and concomitant medications are collected throughout the inpatient stay.

Q15min health checks are done from the time of admission to the time of discharge. Pulse oximetry (pO2) must be monitored throughout the infusion, including during the night when the subject is sleeping. The subject should be awakened if pulse oximetry falls < 91%.

The following priority order will be in effect when more than 1 assessment is required at a particular time point: 1) HAMD17 2) CGI-I/CGI-S 3) EPDS 4) STAI6 5) SSS 6) CSSRS 7) vital signs 8) ECG 9) safety labs and neurosteroid level 10) PK sample 11) neurosteroid level 12) urinalysis drug screen and pregnancy test 13) physical examination

Day 11 and Day 34 visits have visit windows of  $\pm$  3 and  $\pm$  5 days, respectively

# 7.5 Infusion (Day +1) – Cohort 6 (Screening and Admission visits for Cohort 6 described in Section 7.1 and 7.2, respectively)

## 7.5.1 **Before Infusion (Morning of Day +1; Baseline)**

- CTNI to conduct HAMD17 interview
- EPDS
- STAI6
- Assess CGI-S
- Review concomitant medications
- Collect vital signs (BP, pulse, temperature, pulse oximetry, respiratory rate),
- Stanford Sleepiness Scale (SSS)
- Conduct CSSRS interview
- Collect AEs
- Randomization
- The subject's bed should be placed close to the nursing station in an area that allows visual observation of the subject
- Start monitoring of pulse oximetry

## 7.5.2 **During the Infusion and Evening of Day +1 (Day +1)**

- Start 6-hour infusion at 40 mL/hr at 9 am of Day +1 (0h) after baseline assessments are completed (listed above)
- End 6-hour infusion
- Complete +6h assessments after the end of the 6-hour infusion CTNI to conduct interviews for HAMD17 (+6h)
- Conduct interviews for CGI-I (+6h)
- EPDS (+6h)
- STAI6 (+6h)
- Collect AEs
- Collect ECG (+6h)
- Collect VS (BP, pulse, respiratory rate, pulse oximetry, temperature): (+6h)
- Collect SSS (+6h)
- Collect pharmacokinetic samples (+7h [i.e., 1 hour after the end of the infusion], at +10h [i.e., just before the oral dose], and at 1, 2, 3, and 4 hours after the oral dose
- Collect neurosteroid level (+6h)
- Record concomitant medications
- Conduct CSSRS interview (+6h)

CONFIDENTIAL

- Administer the IP: 900 mg of ganaxolone, or matching placebo (four 225 mg capsules or four placebo capsules), at dinner time (i.e., at 7 pm) ±15 minutes of a fatty meal or snack (e.g., fatty yogurt, nuts, avocado)
- Continue monitoring of pulse oximetry and Q15 min health checks

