#### 3.4.5 **Cohort 6**

For Cohort 6, the goal of initiation of treatment with IV infusion followed by oral capsules is to maximize the speed of onset of antidepressant activity while providing the convenience of oral dosing for the remainder of the treatment period. Under this IV-oral dosing schedule there may not be a need for a prolonged inpatient observation.

This initial infusion is targeted to provide a fast onset of antidepressant activity by delivery of rapid plasma exposures to ganaxolone. At dinner time of Day 1 the subjects will take their first oral dose of ganaxolone 900 mg or matching placebo (4 capsules). This dose is expected to provide mean  $C_{max}$  plasma concentrations of approximately 250-300 ng/mL and mean steady-state levels between 90 and 150 ng/mL, which may be mildly sedating. In previous studies ganaxolone has been given up to a daily dose of 2000 mg, and at single doses of 1000 mg. Based on the previous experience this dose is expected to be safe.

At subsequent nights (Days 2-28), the target dose is ganaxolone 900 mg or matching placebo (4 capsules) at dinner time followed by a 3-day taper (3, 2, and 1 capsule/s per day, respectively). However, based on the assessment of the investigator the dose may be maintained at 675 mg or 450 mg (or matching placebo) in case of adverse events, such as grogginess in the morning. In the case of 3 capsules per day on day 28 the taper will consist of 2, 2, and 1 capsule/s on days 29, 30, and 31, respectively. In the case of 2 capsules per day on day 28 the taper will consist of 1 capsule on days 29, 30, and 31. If the subject cannot tolerate 450 mg (or matching placebo) per dose the investigator will contact the Medical Monitor to discuss dosing options.

Subjects will be provided with a diary to capture the details of dose administration and associated food intake throughout the treatment period. Subjects will document the number of capsules taken and whether a fatty meal/snack (e.g., fatty yogurt, nuts, avocado) was consumed  $\pm 15$  minutes of taking the capsules.

The mechanism by which ganaxolone is postulated to be efficacious under this dosing regimen is restructuring of sleep architecture. Preclinical studies have shown that allopregnanolone has the capacity to modulate sleep, and disturbed sleep architecture is one of the hallmarks of depression.

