#### 3.4.6 **Dose justification in context of previous experience with IV ganaxolone**

In Study 1042-0405, which was a Phase 1 study in healthy volunteers investigating the safety of IV ganaxolone, infusion of 30 mg/h for 1 hour, 20 mg over 2 minutes and 20 mg/h for 4 hours led to peak concentrations of 258, 441 and 215 ng/mL, respectively, without any safety concerns. Sedation was assessed using the Modified Observers Assessment of Alertness/Sedation (MOAAS) scale. On this scale, score 5 indicates no sedation (responds readily to name spoken in normal tone) while score 1 indicates deep sedation (responds only after painful trapezius squeeze). In these cohorts, vast majority of the scores were 5 with few exceptions of 4 (lethargic response to name spoken in normal tone) and 3 (responds only after name is called loudly or repeatedly). The sedation scores reversed quickly after the infusion was stopped. The highest bolus dose tested was 30 mg, which was infused over 5-minutes. This dose led to peak concentration levels ( $C_{max}$ ) of > 1,000 ng/mL with no safety concerns (except sedation).

Six subjects reported treatment emergent AEs. No single AE was seen twice. Only one event, headache, was considered by the investigator to be related to ganaxolone. None of the treatment emergent AEs was serious, and all were of mild intensity. No clinically meaningful mean changes in laboratory test results, vital signs, or ECG parameters occurred in any cohort.

This safety profile is consistent with findings from previous studies with the oral formulation of ganaxolone, in which  $C_{max}$  levels of up to 200 to 300 ng/mL were commonly observed and were not associated with major safety findings or toxicity (apart from sedation-related effects).

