#### 6.2.3 **Dosing**

Subjects entering the study will be randomized to ganaxolone or matching placebo at the Baseline Visit. The goal of Cohorts 1-6 is to determine safety, tolerability, PK and efficacy of the IV formulation (and in Cohort 6, the IV formulation followed by oral formulation) of ganaxolone in PPD subjects administered at a predicted dose regimen mimicking the levels of allopregnanolone at the end of pregnancy, or higher.

Infusion rates for ganaxolone IV will be the same as for placebo IV. Cohort 1

The infusion rate for Cohort 1 will be 4 mg/h (16 ml/h of ganaxolone 0.25 mg/ml solution). The infusion rate (4 mg/ml or 16 ml/h) is maintained constant until + 48 hours when the rate is reduced to 2 mg/h and then stopped at + 60 hours.

The infusion rate of 4 mg/ml is estimated to produce a ganaxolone steady state level of about 52 ng/ml after about 24 hours of infusion.

#### Cohort 2

The infusion rate for Cohort 2 will be 8 mg/h (16 ml/h of ganaxolone 0.5 mg/ml solution). The infusion rate (8 mg/ml or 16 ml/h of ganaxolone 0.5 mg/ml solution) is maintained constant until + 48 hours when the rate is reduced to 4 mg/h (8 ml/h of ganaxolone 0.5 mg/ml solution) and then stopped at + 60 hours.

The infusion rate of 8 mg/h is estimated to produce a ganaxolone steady state level of about 100 ng/ml after about 24 hours of infusion.

#### Cohort 3

For Cohort 3, an initial 12 mg bolus of ganaxolone will be given over 2 minutes, followed by ganaxolone infusion administered at a rate of 12 mg/h (24 ml/h of ganaxolone 0.5 mg/ml solution) for 48 hours. The rate is then reduced to 6 mg/h for the next 12 hours. The infusion is stopped at 60 hours.

#### Cohort 4 and 5

Cohort 4 and 5 are optional and will be utilized only if further dose exploration is warranted. The dosing regimen for Cohort 4 and 5 will be decided based on the results of the Cohorts 1-3 and the recommendation of the DRC. However, no bolus doses higher than 16 mg over 2 minutes will be administered. The cap for the maximum infusion rate in Cohorts 4 and 5 will be 16 mg/h.

#### Cohort 6

For Cohort 6, an initial IV infusion 20 mg/h (40 ml/h of ganaxolone 0.5 mg/ml solution or matching placebo) for 6 hours will be followed by oral dose of 900 mg ganaxolone or matching placebo (4 capsules) at dinner time (Day 1). On subsequent nights (Day 2-28) the subject will take 900 mg of ganaxolone, or matching placebo (4 capsules), at dinner time followed by a 3-day

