On Day 1 subjects will have 6 PK samplings: at 1 hour after the end of the 6-hour infusion (i.e., at 4 pm), at 7 pm (just prior to the oral dosing), and at 1, 2, 3, and 4 hours post oral dosing (at 8, 9, 10, and 11 pm) as well at 8 am the following morning (on Day 2) prior to discharge.

The subjects will take a 900 mg dose or placebo (4 caps) on the evening of Day 1 at dinner time and continue with the 900 mg dose or matching placebo at dinner time on Days 2-28. A 3-day taper will follow as described in Section 3.4.6.

A schematic of the study design if provided in Figure 1.

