Start 3-day taper		i la contra c										64	x			.

a Infusion starts at 9 am and ends 6 hours later at 3 pm and is administered at a constant rate of 40 mL/hr.

b Twelve pharmacokinetic samples are collected in Cohort 6:

On Day 1 subjects will have 6 PK samplings: at 1 hour after the end of the 6-hour infusion (i.e., at 4 pm), at 7 pm (just prior to the oral dosing), and at 1, 2, 3, and 4 hours post oral dosing (at 8, 9, 10, and 11 pm) as well at 8 am the following morning (on Day 2) prior to discharge.

A pharmacokinetic sample is also collected on Days 8, 15, 22, 29, and 36 during the study visit.

c All HAMD17 ratings, except the one done at screening, will be conducted by CTNI raters.

 $^{d}$ Q15min health checks are done from the time of start of the infusion to the time of discharge. Pulse oximetry (pO2) must be monitored from the start of the infusion throughout the inpatient period, including during the night when the subject is sleeping. The subject should be awakened if pulse oximetry falls < 91%.

e On Day +1 all efficacy assessments should be conducted first before lab draws, if possible.

f All Day +2 assessments, including PK and neurosteroid levels, are to be done before the subject is discharged from the unit.

The following priority order will be in effect when more than 1 assessment is required at a particular time point: 1) HAMD17 2) CGI-I/CGI-S 3) EPDS 4) STAI6 5) SSS 6) CSSRS 7) vital signs 8) ECG 9) safety labs and neurosteroid level 10) PK sample 11) neurosteroid level 12) urinalysis drug screen and pregnancy test 13) physical examination

All outpatient visits have  $a \pm 3$ -day visit window, except Visits 3 and 5 which have just  $a \pm 1$ -day visit window and Visits 4 and 6 which have  $a \pm 2$ -day visit window.

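### Cohort 6 schedules no SSS, blood pressure, respiratory rate or ECG reading during the 20 mg/h infusion or 1-4 h after the first 900 mg dose, so scored safety data may understate peak effects

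*Protocol*

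**What the plan says.** Protocol 2.2.1 names adverse events, laboratory measures, vital signs, CSSRS, ECG, SSS and physical examination as the safety measures, and says Cohort 6 uses the same ones as Cohorts 1-5. Section 6.2.4 names sedation and dizziness as known effects at higher doses.

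For Cohort 6:

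- Table 2 notes: "Infusion starts at 9 am and ends 6 hours later at 3 pm and is administered at a constant rate of 40 mL/hr". At 0.5 mg/ml that is 20 mg/h. Cohorts 1-3 run at 4, 8 and 12 mg/h, and Cohorts 4-5 are capped at 16 mg/h (boluses aside).
- Section 7.5.2 lists SSS, vital signs and ECG once each after baseline on Day 1, at +6h, under the instruction "Complete +6h assessments after the end of the 6-hour infusion".
- The Table 2 priority order when assessments coincide begins "1) HAMD17 2) CGI-I/CGI-S 3) EPDS 4) STAI6 5) SSS 6) CSSRS 7) vital signs 8) ECG".
- The first oral dose is given at about 7 pm. Section 3.4.5 expects it to give mean peak "plasma concentrations of approximately 250-300 ng/mL and mean steady-state levels between 90 and 150 ng/mL, which may be mildly sedating". PK is drawn at 8, 9, 10 and 11 pm. The next SSS, vital signs and ECG belong to the Day 2 pre-discharge set (7.5.3).

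Section 3.5 supports the inpatient start on the ground that it lets staff observe the effects of both the infusion and the first oral dose. On sedation in the healthy-volunteer IV study, section 3.4.6 reports: "The sedation scores reversed quickly after the infusion was stopped".

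**The concern.** The two periods that the inpatient stay exists to observe are the infusion at the top rate and the hours after the first 900 mg dose. Neither contains a scheduled SSS, blood pressure, respiratory rate or ECG reading. The one Day 1 set comes after the infusion has stopped and behind four efficacy scales. If sedation eases soon after an infusion stops, as it did in the healthy-volunteer study, the SSS that the SAP tabulates (SAP 7.2.5 and 12.6.4.4) may show less sedation than the women had while the drug was running. The same could apply to blood pressure and ECG. Protocol 2.1 and 3.2 say the results will be used to choose a dose and regimen, so the scored tolerability data for this cohort matter.

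**Working it through.** No sample size or power figure bears on this point. The check is clock arithmetic and a count of scheduled readings.

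**Clock, with 0h = 9 am (Table 2 notes).** End of infusion: 9 am + 6 h = 3 pm (+6h). First oral dose at 7 pm: +10h. PK draws at 8 to 11 pm: +11h to +14h. Day 2 PK at 8 am: 15 h to midnight + 8 h = +23h, which reproduces the 23h printed in Protocol 7.5.3.

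**Count of scheduled post-baseline readings (7.3.2, Table 1 notes, 7.5.2, Table 2).**

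| | Cohorts 1-5, before +60h | Cohort 6, during infusion | Cohort 6, 1-4 h after first oral dose |
|---|---|---|---|
| SSS | 3 (+8h, +32h, +56h) | 0 | 0 |
| Vital-sign set | 9 (+4h to +56h) | 0 | 0 |
| ECG | 3 (+12h, +24h, +48h) | 0 | 0 |

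A 60-hour and a 6-hour infusion cannot be compared by raw count; what matters is zero against some. The +56h readings in Cohorts 1-5 are at half rate, because the rate is lowered at +48h. In their first 6 hours Cohorts 1-5 have only the +4h vital signs. Vital-sign set here means the scheduled set; oximetry is continuous in both groups.

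**Gaps.**

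- From the +6h set to the Day 2 set: 23 - 6 = 17 h, if the Day 2 set is done at 8 am. Only the PK sample has that clock time.
- From the oral dose to the Day 2 set: 23 - 10 = 13 h. With the dose between 6 and 8 pm (the stated ±1 hour) and the Day 2 set between 6 am and noon (assumption), the range is 10 to 18 h.
- The documents give no time of peak for the oral dose. For any peak within the sampled 1-4 h, no scheduled SSS, vital-sign set or ECG falls near it.

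**How much could have eased by the +6h SSS?** The documents give no half-life, reversal time or scale duration, so this cannot be computed. As an illustration, assume the four scales take 0.5 to 1 h and the level falls exponentially. Fraction remaining = 0.5^(delay / half-life).

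| Assumed half-life | After 0.5 h | After 1 h |
|---|---|---|
| 0.25 h | 25% | 6% |
| 1 h | 71% | 50% |
| 4.8 h | 93% | 87% |

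The 4.8 h row takes the 24 h to steady state in Protocol 3.4.1 divided by 5 half-lives. The result runs from almost everything gone to almost nothing gone, so the direction of any bias is plausible and its size is unknown.

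**Analysis window.** SAP 8.4 gives Cohort 6 one Day 1 (Post-Infusion) row, covering all of Study Day 1 from Study Time 0 onward, and uses the latest value in a window. A reading in the last 30 minutes of the infusion still falls in that row. An added evening reading would fall there too and would replace the +6h value.

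**The case against.** The strongest reply is that sedation is not missed. Oximetry is continuous from the start of the infusion through the night, and a value below 91% triggers an assessment for sedation (Protocol 7.8.5.4). Health checks run every 15 minutes, the bed is placed for visual observation, and adverse events are collected on Day 1 and tabulated by treatment group, severity and relatedness for each cohort (Protocol 9.5.7, SAP 12.6.1). All of that stands. The gap is in scored data, not in care or in the adverse event record.

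Stronger readings that a reader might infer do not hold:

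- **That the protocol says sedation has reversed by the time it is scored.** Section 3.4.6 reports quick reversal on a different scale, in healthy volunteers, with no time given. It says nothing about the +6h SSS.
- **That the same applies to the oral dose.** Section 3.4.6 concerns IV dosing. Sections 3.4.5 and 6.2.4 name morning grogginess or sedation as effects of the evening dose, and the Day 2 SSS can catch those.
- **That the sedation dose-response across cohorts is confounded with timing.** SAP 12.0 tabulates by treatment group within cohort, against concurrent placebo assessed at the same times. No cross-cohort SSS analysis is specified.
- **That Cohorts 1-5 are timed to peak exposure.** Cohort 3's bolus is expected to reach 300 ng/ml briefly, yet its first vital signs are at +4h and its first SSS at +8h.

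Four evening SSS ratings up to 11 pm would also pick up ordinary bedtime sleepiness, so a dense evening schedule is not warranted.

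**Conclusion.** The scheduling facts hold. In Cohort 6 no post-baseline SSS, blood pressure, respiratory rate or ECG is scheduled during the 20 mg/h infusion, and none 1-4 h after the first 900 mg dose. The +6h set comes after the infusion and after four efficacy scales. The scored safety data may therefore understate peak effects; the documents do not show that they will, and the size cannot be estimated from them. The 17-hour gap assumes a Day 2 set at 8 am. The point does not undermine the adverse event evaluation or the comparison with placebo at the times measured. It is a modest weakness in the measures that the safety objective names, and it is cheap to correct.

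**What to change.** In Protocol 7.5.2 and the Table 2 notes, take the existing +6h SSS, vital signs and ECG in the last 30 minutes of the infusion, before it is stopped and before the efficacy scales, and state this as an exception to the priority order. The window is long enough: vital signs need 5 minutes supine, the ECG 10 minutes of rest, and the SSS is a single self-rating. The note asking for efficacy assessments before laboratory draws on Day 1 is unaffected. Appendix 3 shows that a preceding protocol version had the infusion stopped only after the +6h assessments. That is not an inconsistency, but it suggests the timing is workable. No new SAP window is needed, though the Post-Infusion label would no longer describe these readings.

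Optional: add one SSS and vital-sign reading at an existing early-evening PK draw. If so, split the Day 1 (Post-Infusion) row in SAP 8.4, so that the latest-value rule does not overwrite the +6h reading.

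Cost: a small change in assessment order and a protocol amendment with IRB/EC approval. Women already dosed will lack the re-timed reading, so the tables should distinguish the two timings. The optional part adds a short procedure, some eCRF fields and a SAP change.
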